6.5.6.1.1 Output Data

Data will be transferred to the responsible Biostatistics representative, or their designee, and incorporated into standard formats following the Study Data Tabulation Model (SDTM). Data will then be mapped to analysis datasets using the Analysis Data Model (ADaM) standard. Both SDTM- and ADaM-formatted data will be used to create the subject data listings, while all tables and figures will be based on the ADaM-formatted data.

SDTM will follow the SDTM Version 1.7 model and will be implemented using the SDTM Implementation Guide Version 3.3 and the most recent version of SDTM Controlled Terminology at the time of study start. ADaM data will follow the ADaM Version 2.1 model

and will be implemented using the ADaM Implementation Guide Version 1.1. Both SDTM and ADaM will be validated using Pinnacle 21. Any discrepancies in the validation will be noted in reviewer's guides accompanying the final data transfers.

The define.xml descriptive document will be created for SDTM and ADaM using the Define-XML Version 2.0 model.

6.5.6.2 Primary Effectiveness Endpoints

The primary effectiveness endpoints at the time of refractive stability are the following:

- The percentage of eyes that achieve predictability (calculated as postoperative refraction minus targeted refraction. If targeted refraction is emmetropic, then it is equal to postoperative refraction) of MRSE within ± 0.50 D
- The percentage of eyes that achieve predictability of MRSE within \pm 1.00 D
- The percentage of eyes targeted for emmetropia that achieve a UCDVA of 20/40 (logMAR of 0.3) or better

The primary effectiveness endpoints will be analyzed for all treated eyes with missing data imputed using multiple imputation (MI) Fully Conditional Specification (FCS) methodology. Similarly, the categorical summaries of logMAR UCDVA will be presented for treated eyes that were targeted for emmetropia which had low to moderate preoperative myopia and, separately, for eyes which had high preoperative myopia.

For the primary effectiveness endpoints, data imputation employing MI method will be performed on missing MRSE, or logMAR UCDVA values at the time of refractive stability, as recorded in the eCRF, using the SAS[®] procedure PROC MI by applying the following SAS[®] code for treated eye:

```
PROC MI DATA=INDATA SEED=1562379 NIMPUTE=20 OUT=OUTDATA1;
BY PARAM EYE;
FCS;
VAR VISIT4 to VISIT8 ;
RUN;
```

where

- *INDATA* is the name of the input dataset
- OUTDATA1 is the name of the output dataset containing twenty 'complete' datasets
- PARAM = MRSE and UCDVA
- VISIT4 to VISIT8 holds post-operative values at Week 1, Month 1, Month 3, Month 6, and Month 9, respectively for each of the analysis variables

The logMAR values will be converted to Snellen scores as follows:

Log MAR	Snellen Score
1.7	20 / 1000
1.6	20 / 800
1.5	20 / 630
1.4	20 / 500
1.3	20 / 400
1.2	20 / 320
1.1	20 / 250
1	20 / 200
0.9	20 / 160
0.8	20 / 125
0.7	20 / 100
0.6	20 / 80
0.5	20 / 63
0.4	20 / 50
0.3	20 / 40
0.2	20 / 32
0.1	20 / 25
0	20 / 20
-0.1	20 / 16
-0.2	20 / 12.5
-0.3	20 / 10

Once Δ MRSE and logMAR UCDVA are derived for all observations and the observations are categorized into response variables according to various MRSE and UCDVA thresholds

(e.g., MRSE within \pm 1.00 D), the imputed datasets are used to obtain the percentage of eyes that achieve MRSE predictability or UCDVA of 20/40 or better as follows:

PROC FREQ DATA=OUTDATA1; TABLES CRITERIA / BINOMIAL; BY IMPUTATION ; ODS OUTPUT BINOMIAL=PROP; RUN; DATA OUTDATA2; MERGE PROP (WHERE=(Label1="Proportion") RENAME=(nValue1=PROP)) PROP (WHERE=(Label1="ASE") RENAME=(nValue1=PROP SE)); BY IMPUTATION ; RUN; PROC MIANALYZE DATA=OUTDATA2; MODELEFFECTS PROP; STDERR PROP SE; BY VISIT; ODS OUTPUT PARAMETERESTIMATES=ESTIMATES; RUN;

where

- OUTDATA1 is the output dataset from PROC MI
- *CRITERIA* is a responder variable (either achieving MRSE predictability or UCDVA of 20/40 or better)
- OUTDATA2 is the output dataset containing the estimated proportion of responders and the standard error
- ESTIMATES is the results dataset

6.5.6.2.1 Primary effectiveness endpoint hypothesis testing

All hypotheses will be tested at the one-sided 2.5% (α =0.025) level of statistical significance.

6.5.6.2.1.1 Percentage of eyes that achieve predictability of MRSE within ± 0.50 D at the time of refractive stability

The null hypothesis (H₀) is that the proportion of eyes that achieve predictability within \pm 0.50 D (π) is less than or equal to 0.80 (80%) at the time of refractive stability. The alternative hypothesis (H₁) is that the proportion is greater than 0.80 (80%).

$$H_0: \pi \le 0.80$$

 $H_1: \pi > 0.80$

The above hypothesis will be tested using CI calculated using normal approximation for binomial proportion. If the lower limit of the CI is above 0.8, then test is deemed significant.

6.5.6.2.1.2 Percentage of eyes that achieve predictability of MRSE within ± 1.00 D at the time of refractive stability

The null hypothesis (H₀) is that the proportion of eyes that achieve predictability within \pm 1.00 D (π) is less than or equal to 0.90 (90%) at the time of refractive stability. The alternative hypothesis (H₁) is that the proportion is greater than 0.90 (90%).

$$H_0: \pi \le 0.90$$

 $H_1: \pi > 0.90$

The above hypothesis will be tested using CI calculated using normal approximation for binomial proportion. If the lower limit of the CI is above 0.9, then test is deemed significant.

6.5.6.2.1.3 Percentage of eyes targeted for emmetropia that achieve UCDVA of 20/40 or better at the time of refractive stability

The null hypothesis (H₀) is that the proportion of eyes targeted for emmetropia and that achieve UCDVA of 20/40 or better at the time of refractive stability (π), is less than or equal to 0.88 (88%). The alternative hypothesis (H₁) is that the proportion is greater than 0.88 (88%).

$$H_0: \pi \le 0.88$$

 $H_1: \pi > 0.88$

The above hypothesis will be tested using CI calculated using normal approximation for binomial proportion. If the lower limit of the CI is above 0.88, then test is deemed significant.

6.5.6.2.1.4 Statistical Success Criteria for the Study

The study will be statistically successful if all primary effectiveness endpoints in this section are analyzed successfully (i.e., if the null hypotheses are rejected for all primary effectiveness endpoints) at the visit when cohort refractive stability is achieved.

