7.0 MANIFEST REFRACTION

It is essential that a consistent and standard procedure be used to obtain manifest refraction (MR) measurements. These measurements will be obtained by a qualified ophthalmologist, optometrist, or trained ophthalmic technician only. At no time during the study will auto-refraction be utilized as a final endpoint refraction. Auto-refractor or lensometer readings may only be

utilized to obtain a starting point for the refraction if necessary. The manifest refraction is considered to be the subjectively determined refraction which provides the best corrected visual acuity at a distance of optical infinity.

Each subject must be manually refracted to his/her best correction by an ophthalmologist, optometrist, or a skilled technician using the ETDRS chart at 4 meters with a phoropter or trial frame under photopic lighting conditions. All refractions will be conducted in a manner consistent with the site's standard techniques using 0.25 D steps and utilizing a Jackson cross cylinder method. The resulting manifest refraction obtained using the ETDRS chart at 4 meters is adjusted for optical infinity by subtracting 0.25 D from the sphere value. The 'Chart R' with Sloan letters will be used to obtain the manifest refraction. The manifest refraction which has been adjusted for optical infinity will be documented on the Sponsor-supplied refraction worksheet. The manifest refraction which has been adjusted for optical infinity should be used as the basis for laser refractive treatment.

The resulting manifest refraction will be placed in a trial frame and utilized to obtain BSCVA results. For testing at 4 meters, a +0.25 D must be added to the manifest refraction to correct the testing distance to optical infinity. If for some reason (e.g., dense cataract), MR cannot be obtained, the results should be documented as ND as indicated above and not entered as zeros. In the event of this occurrence, BSCVA will not be tested and the reason for ND will be required in the source document and in the eCRF.

NOTE: Contact lens wearers need to demonstrate a stable refraction (within \pm 0.50 D) in the operable eye(s), as determined by MRSE on two consecutive exam dates. Stability of the refraction is determined under the following conditions:

- Lenses are not worn for at least 2 weeks (rigid or toric contact lenses) or 3 days (soft contact lenses) prior to the first refraction used to establish stability and through the day of surgery;

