4 INTRODUCTION

The purpose of this statistical analysis plan (SAP) is to describe the planned analyses and reporting for clinical study Bausch & Lomb 884 conducted according to TENEO 317 Clinical Investigation Plan, Version 8.0, dated 19 November 2020.

This SAP is being written with due consideration of the recommendations outlined in the most recent International Conference on Harmonisation (ICH) E3 Guideline (July 1996), entitled Guidance for Industry: Structure and Content of Clinical Study Reports.

This SAP describes the data that will be analyzed and the subject characteristics, device effectiveness, and safety assessments that will be evaluated.

This SAP provides details of the specific statistical methods that will be used. The statistical analysis methods presented in this document will supersede the statistical analysis methods described in the clinical protocol. If additional analyses are required to supplement the planned analyses described in this SAP, they will be completed and will be identified in an amended SAP (approved prior to database lock) or in the clinical study report.

Device Description

The Technolas Teneo 317 Model 2 (ver. 1.28 US software [SW]) excimer laser is a scanning excimer laser that operates at 193 nm ultraviolet wavelength to photoablate corneal tissue and employs a proprietary aspheric ablation profile rather than a conventional "Munnerlyn" ablation profile. By scanning a small diameter beam (1 mm in diameter) in a random raster pattern, the Teneo 317 Model 2 (ver. 1.28 US SW) excimer laser offers the following advantageous features:

- Flexible treatment patterns for the treatment of myopia,
- Wide ablation zones (up to 7 mm), and
- A smooth ablation-surface.

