6.5.6 Analysis of Effectiveness Endpoints

6.5.6.1 Descriptive Statistics and Data Preparation

Statistical programming and analyses will be performed using SAS® Version 9.4 or higher. Output will be provided in rich text format (RTF) for tables and portable document format (PDF) for tables, data listings, and figures using landscape orientation. All study data will be listed by subject, eye, and visit (as applicable) based on all treated subjects unless otherwise specified.

Summaries for continuous and ordinal variables will include the number of observations (n), arithmetic mean, standard deviation (SD), median, minimum, and maximum. Minima

and maxima will be reported with the same precision as the raw values; means and medians will be presented to one additional decimal place than reported in the raw values. Standard deviations will be presented to two additional decimal places than reported in the raw values. Summaries for discrete variables will include counts and percentages. All percentages will be rounded to one decimal place (i.e., XX.X%).

When summarized by visit, nominal visits as indicated on the case report forms will be used. Visit windows will not be considered in the presentation of data by visit.

All statistical tests will be one-sided with a significance level of 0.025 ($\alpha = 0.025$) unless otherwise specified.

Confidence intervals (CIs) around single estimated proportions will be two-sided at 95% confidence.

All p values will be rounded to 4 decimal places; p-values less than 0.0001 will be presented as "<0.0001"; p-values greater than 0.9999 will be presented as ">0.9999."

Unless otherwise specified, summaries will be presented by visit, where appropriate. Data listings will be sorted by subject number, eye, visit/time point, and parameter as applicable.

Baseline is defined as the last measurement prior to LASIK surgery. Change from baseline will be calculated as post-baseline visit minus baseline visit.

Eyes will be treated as independent sampling units ignoring any correlation between the two eyes of each subject, as is customary for LASIK clinical trials.

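### The normal-approximation limit that decides each primary endpoint does not hold the stated one-sided 2.5% level: its exact size with complete data is 3.2% to 4.7%

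*SAP*

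**What the plan says.** SAP 6.5.6.2.1 fixes the level: "All hypotheses will be tested at the one-sided 2.5" per cent level. For each endpoint it then gives the rule: "The above hypothesis will be tested using CI calculated using normal approximation for binomial proportion". Success means a lower limit above 0.80 (MRSE within 0.50 D), 0.90 (MRSE within 1.00 D) or 0.88 (UCDVA 20/40 or better). SAP 6.5.6.1 says that intervals "around single estimated proportions will be two-sided at 95% confidence".

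The code in SAP 6.5.6.2 shows which standard error is used. It reads the PROC FREQ proportion and its ASE from each of 20 imputed datasets ("OUTDATA2 is the output dataset containing the estimated proportion of responders and the standard error") and pools them in PROC MIANALYZE. The endpoints are "analyzed for all treated eyes with missing data imputed using multiple imputation (MI) Fully Conditional Specification (FCS) methodology". On the two eyes of one subject, SAP 6.5.6.1 states: "Eyes will be treated as independent sampling units ignoring any correlation between the two eyes of each subject".

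Other parts of the plan name other tests. Protocol 9.3.2 to 9.3.4 and SAP 6.5.9.2 to 6.5.9.4 state power for a one-group chi-square test at one-sided 2.5%. The Protocol synopsis names a binomial test after imputation. The SAP governs: "The statistical analysis methods presented in this document will supersede the statistical analysis methods described in the clinical protocol".

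**The concern.** The ASE is the square root of p(1-p)/n at the observed p. To pass, the observed p must lie above a null of 0.80 to 0.90, and there p(1-p) is smaller than its null value. The limit is therefore too short on the side that decides success, and the false-positive rate exceeds the level promised one sentence earlier.

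At stake is a pre-specified error rate in a pivotal study. In addition, the test that decides success is not the test for which power was stated.

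**Working it through.** **Inputs.** Nulls 0.80, 0.90, 0.88; one-sided 2.5%; two-sided 95% limit (z = 1.96); planning rates 0.945, 0.99, 0.99 at n = 300 (SAP 6.5.9); about 334 treated eyes with losses up to 10% (SAP 6.5.9.5); independent eyes (SAP 6.5.6.1).

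**1. The plan's power figure.** For the chi-square test, power = Phi{[(p1-p0)√n - 1.96√(p0(1-p0))] / √(p1(1-p1))}.

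- 0.50 D: (0.145 × 17.32 - 1.96 × 0.400) / 0.228 = 7.6
- 1.00 D: (0.09 × 17.32 - 1.96 × 0.300) / 0.0995 = 9.8
- UCDVA: (0.11 × 17.32 - 1.96 × 0.325) / 0.0995 = 12.7

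All three exceed 99.99%, as stated. Exact binomial power is also above 99.99% under the Wald and score pass marks.

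**2. Pass marks at n = 300.** Wald: p - 1.96√(p(1-p)/n) > p0. Score: (p - p0)/√(p0(1-p0)/n) > 1.96.

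| Endpoint | Wald mark | Wald SE | Lower limit | Null SE | Score z at the Wald mark | Score mark |
|---|---|---|---|---|---|---|
| 0.50 D | 253 (0.8433) | 0.0210 | 0.8022 | 0.0231 | 1.88 | 254 |
| 1.00 D | 279 (0.9300) | 0.0147 | 0.9011 | 0.0173 | 1.73 | 281 |
| UCDVA | 274 (0.9133) | 0.0162 | 0.8815 | 0.0188 | 1.78 | 276 |

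Each Wald mark passes the SAP rule but falls short of 1.96 on the null standard error.

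**3. Exact size.** This is the binomial probability, at p0, of reaching the mark (complete data, independent eyes).

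| n | Rule | 0.50 D | 1.00 D | UCDVA |
|---|---|---|---|---|
| 300 | Wald (253/279/274) | 3.28% | 4.58% | 4.12% |
| 300 | Score (254/281/276) | 2.30% | 1.71% | 1.66% |
| 334 | Wald (281/310/305) | 3.18% | 4.75% | 3.32% |
| 334 | Score (282/312/306) | 2.28% | 1.90% | 2.17% |

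An exact binomial test has the same marks as the score test at both sizes. At all 81 sample sizes from 270 to 350 the Wald size is above 2.5%: 2.9-4.0%, 3.3-5.3% and 3.1-4.8%.

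**4. Size under imputation.** The documents do not fix the outcome distribution or the share missing, so this step rests on assumptions: n = 334 in two strata of 167 (imputation by eye), the stability visit plus two earlier visits, normal errors, visit correlation 0 to 0.9, values missing completely at random, 20 imputations, Rubin t limits. Monte Carlo error is about 0.1 point. SAS was not run.

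Rounding matters. Refraction is taken "using 0.25 D steps and utilizing a Jackson cross cylinder method" (Protocol Appendix B 7.0), so MRSE falls on 0.125 D steps, and SAP 6.5.6.2 rounds logMAR to one decimal. The PROC MI code shows no rounding of imputed values. Left unrounded, they pass less often than recorded ones.

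| Wald size | Missing | 0.50 D | 1.00 D | UCDVA |
|---|---|---|---|---|
| Imputed on the recorded scale | 2% | 3.2-3.3% | 3.7-4.1% | 3.7-4.0% |
| | 5% | 2.9-3.1% | 3.6-3.8% | 3.4-3.6% |
| | 10% | 2.5-2.9% | 3.1-3.5% | 3.2-3.4% |
| Imputed, unrounded | 2% | 2.7-2.9% | 3.5-3.8% | 3.2-3.4% |
| | 5% | 2.1-2.2% | 3.0-3.3% | 2.6-2.9% |
| | 10% | 1.4-1.6% | 2.2-2.6% | 1.8-2.0% |

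Over the same cells the pooled null-variance score test has size 0.9-2.3%.

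**5. Study level, complete data.** All three endpoints must pass (SAP 6.5.7.5), so the study-level error cannot exceed the largest single size.

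- 0.50 D at its null: with centred normal errors, SD = 0.50/1.2816 = 0.39 D, so 99.0% lie within 1.00 D. With UCDVA at 0.99, the study error is 3.3% (n = 300) or 3.2% (n = 334).
- 1.00 D at its null, same shape: only 58.9% lie within 0.50 D, and the study almost never passes.
- UCDVA at its null: at most 4.1% or 3.3%.

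**6. Chance of a different decision, n = 300.** Below 1e-10 per endpoint at the planning rates. At most 6%, 18% and 16%, reached if the true rates are 0.843, 0.932 and 0.915.

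**The case against.** The strongest reply is that the complete-data sizes describe an analysis the SAP does not use to decide. The primary test follows imputation, and with 10% missing and unrounded imputed values the Wald rule is already at or below 2.5%, or within 0.1 point of it. There the score test moves further below the level. Under other assumed settings (correlation 0.5; UCDVA SD 0.15 logMAR; 10% missing; unrounded) the Wald sizes were 1.8%, 2.2% and 1.0%, against 1.1%, 1.1% and 0.5% for the score test. Protocol 9.6.2 also already foresees pooling proportions with their standard errors, so the SAP rule is an open implementation of it. The largest excess belongs to the 1.00 D endpoint, which seldom drives the joint decision, and the planning rates are far from the pass marks.

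Much of this stands. The size under imputation depends on assumptions, the score test is conservative there, and the practical effect is slight. It does not rescue the stated level. With little missing data the excess remains whether or not values are rounded; with rounding it remains for 1.00 D and UCDVA even at 10% missing. Where it disappears, it does so through an unstated coding choice. A test below 2.5% keeps the promise made in the SAP; one above it does not. Requiring all three endpoints to pass removes the need for a multiplicity adjustment but does not correct the size of any one test.

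**Conclusion.** The concern holds. The SAP promises one-sided 2.5% and uses a rule with exact size 3.2% to 4.7% at the two planned sample sizes, given complete data and the SAP's own independence assumption. Under imputation the simulated size runs from 1.4% to 4.1%, depending on the share missing and on rounding; that range is less certain than the enumeration. With normal errors and 0.50 D at its null, the study-level error is about 3.2-3.3%.

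The stated power is correct, but for another test; it holds for the Wald rule as well. The outcome would change only if a result fell within 1 or 2 eyes of the pass mark, which is very unlikely at the planning rates. This should be corrected, but it does not threaten the design. Correlation between fellow eyes is a separate matter.

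**What to change.** - **SAP 6.5.6.2.1:** replace the normal-approximation limit with a score test using the null variance, which matches the chi-square test in SAP 6.5.9 and Protocol 9.3. Pool it as T = p0(1-p0)/n + (1 + 1/20)B, where B is the between-imputation variance. Compare (pooled p - p0)/√T with the upper 2.5% point of t on Rubin's degrees of freedom, or of the normal if B = 0.
- **SAP 6.5.6.2:** state whether imputed MRSE and logMAR values are rounded to the recorded step before classification. At 10% missing this moves the Wald size by about 1 to 1.5 points.
- **SAP 6.5.6.3:** name an exact binomial limit for the unimputed observed-case, best-case and worst-case analyses.
- **Wording:** use one test name in the Protocol synopsis and SAP 6.5.9, and list the change in SAP 6.6.

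The cost is SAP wording and a few lines of code. At 300 eyes the pass mark rises by 1 eye (0.50 D) or 2 eyes (1.00 D, UCDVA), and complete-data power stays above 99.99% under independence. The change brings the size to about 2.5% or below, not to exactly 2.5%. With complete data the score test slightly exceeds 2.5% at 17, 6 and 10 of the 81 sizes (at most 2.7%), and under imputation it is conservative.

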6.5.6.3 Sensitivity Analyses of Primary Effectiveness Endpoints

As sensitivity analyses, the primary effectiveness endpoints will be assessed at the time of cohort refractive stability based on the original dataset (rather than imputed datasets) using the following analyses:

- Observed case analysis: Subjects with both targeted and observed MRSE values available will be used for analysis. Subjects with a non-missing logMAR UCDVA value will be used for analysis. Missing values will not be included in the analysis.
- Best case analysis: Subjects with missing MRSE values will be imputed as "MRSE within ± 0.50" and "MRSE within ± 1.00". Subjects with missing logMAR UCDVA values will be imputed as "UCDVA 20/40 or Better". Subjects with missing values will be imputed as meeting each criterion mentioned above (counted in both the numerator and denominator in percentage calculations).
- Worst case analysis: Subjects with missing MRSE values will be imputed as "MRSE not within ± 0.50" and "MRSE not within ± 1.00". Subjects with missing logMAR UCDVA values will be imputed as "UCDVA Worse than 20/40". Subjects with missing values will be imputed as not meeting each criterion mentioned above (counted in the denominator only in percentage calculations).
- Poolability analysis: The proportion of subjects meeting the MRSE or UDVA criterion will be presented by site and visit without imputation. At each visit, a chi-squared test will be used to test for statistically significant differences among the sites. When a chi-squared test is not appropriate due to sparse data, then a Fisher's exact tests may be substituted.

6.5.6.3.1 Predictability and Refractive Stability Analyses

The following predictability and refractive stability descriptive summaries will be provided for each visit interval starting with the 1- to 3-month interval and continuing to the 6- to 9month interval for all treated eyes, eyes treated for spherical myopia, and eyes treated for astigmatic myopia unless otherwise specified. Stability analysis will be repeated for Consistent Cohort.

- Eyes that exhibit an absolute change of less than or equal to 0.50 D, 1.00 D, and 2.00 D of MRSE between two refractions performed at 1 month and 3 months, and between subsequent refractions performed at least 3 months apart.
- Mean overall change and change per month (calculated as, Difference in MRSE/ Duration in Months, where month = 30 days) in MRSE between consecutive scheduled visits as determined by a paired analysis, with 95% CIs around the mean rate of change based on t-distribution.
 - The mean rate of change in MRSE is expected to decrease monotonically over time, with a projected asymptote of zero or a rate of change attributable to normal aging.
 - The 95% CI for the mean rate of change in MRSE is expected to include zero or a rate of change attributable to normal aging.
- Mean (\pm SD) MRSE for the preoperative and each postoperative visit
- Proportion of eyes with residual astigmatic error (absolute shift from Preoperative Visit to each postoperative visit in manifest axis versus residual manifest cylinder magnitude calculated as postoperative cylinder value minus targeted cylinder value in categories of ± 0.5 D, ± 1.0 D, ± >1.0 D) will be presented in a table and also stratified by preoperative diopter of cylinder as specified in Table 1 at Month 1, Month 3, Month 6, and Month 9 for eyes treated for astigmatic myopia.
- Assessment of cylinder stability between two refractions performed at 1 month and 3 months, and between subsequent refractions performed at least 3 months apart for correction of spherocylindrical refractive errors, expressed as the proportion of eyes

with an absolute change in cylinder magnitude of 0.00 D, 0.01 D to 0.50 D, 0.51 D to 1.00 D, 1.01 D to 1.50 D, and >1.51 D.

- Vector magnitude correction analysis will be summarized including intended refractive correction (IRC), surgically induced refractive correction (SIRC) and correction ratio (CR) calculated as SIRC/IRC, as defined in the Eydelman M paper
 [2] and also provided in the appendix. These data by study visit will be presented as continuous summary for all eyes treated for astigmatic myopia.
- Cylinder correction (non-vectorial) stratified by preoperative cylinder as specified in Table 1 for all eyes treated for astigmatic myopia will be summarized on a continuous scale in a table by study visit beginning at Month 1 for percent reduction of absolute IRC.

